The steering committee will work with the patient partner and the patient advisory group to ensure that the language describing the metrics is understandable to a general audience with at least grade six education, particularly for the process metrics. Within the Delphi survey, for each metric there will be a brief description of what it is and why it might be important, and expandable links for further explanation and details for each metric (e.g., the items for a patient-reported outcome or experience measure), as deemed necessary by the steering committee.

Stage 2. Modified Delphi consensus process

Study Population

We aim to recruit 77 participants with the following characteristics (accounting for 30% attrition rate (9,17)):

- 26 anesthesiologists
- 26 patients and/or their family members/caregivers
- 9 surgeons, one from each of the following specialties (may include clinician-researchers):
 - General surgery
 - Neurosurgery
 - Obstetrics and gynecology
 - Orthopedic surgery
 - Otolaryngology
 - Plastic surgery
 - Thoracic surgery
 - Urology
 - Vascular surgery
- 4 nurses
- 8 physicians: 2 each from internal medicine, emergency department, family practice, family practice anesthetists
- 4 health administrators or quality improvement leads

Inclusion Criteria: Adult participants aged 18 and above will be included. Patient/family participants must have undergone a surgical experience within the past three years, and have the capacity to provide informed consent. All other participants must be actively practising in Canada in the disciplines they represent.

Exclusion Criteria: Participants with self-declared conflicts of interest with this project.

While the study will primarily be conducted in English using BC Children's Hospital Research Institute's REDCap survey system (18,19), to ensure representation, participants will not be excluded based on language or technology limitations. During recruitment, patients could indicate accommodations required, including translation and submitting study materials through postal mail. The steering committee will review the degree to which accommodations would be feasible within the human resources and study budget.

Development of a standardized set of core metrics to assess the quality of anesthesia, perioperative care, and acute pain management in Canada: scoping review and multidisciplinary consensus Delphi study

Recruitment, consent, panel selection, and withdrawal

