
The multidisciplinary panel of participants will iteratively review the list of candidate metrics using a modified Delphi process. While specific guidance on consensus thresholds and the optimal scales are limited, the design will follow best practices from literature (3,6-11). In the last Delphi cycle, the panel will be asked to select the most essential items to include into a core set of metrics.

Independent, anonymous voting using REDCap over three rounds will be used to identify the most important metrics to define the quality of anesthetic care. Each round will be coordinated through the Department of Anesthesiology, Pharmacology and Therapeutics, Faculty of Medicine, UBC.

Participants will be given at least two weeks of notice about an upcoming round, and will have two weeks to complete the REDCap survey for a given round. Reminder emails will be sent 7 and 14 days after the survey opens to those who have not yet completed it. If a survey is still not completed, up to two additional reminders will be sent once a week, and if still no response, the round will be closed. The participant who missed a round will still be able to participate in future rounds. There will be at least two weeks between each round to provide time for the steering committee to analyze the data and prepare for the next round. Additional cycles (beyond the 3rd) may be performed if the objectives have not been achieved.

Delphi Round 1

The initial list of metrics and descriptions from the scoping review will be presented. Participants will independently score each of the listed metrics for importance on a five-point scale (from '1=not at all important' to '5=very important') (8). Participants may also enter comments in free-text if they have any specific feedback or suggestions on a given item, which will be summarized and shared with participants in Round 2. The mean and median scores for each metric will be calculated for overall panel and for subgroups of 1)

Development of a standardized set of core metrics to assess the quality of anesthesia, perioperative care, and acute pain management in Canada: scoping review and multidisciplinary consensus Delphi study

patient/caregiver and 2) health provider groups, and will also be presented in Round 2. Metrics receiving a mean score ≥ 4 by $\geq 65\%$ of each subgroup and ≤ 2 by $<20\%$ of the subgroups will be retained for voting in Round 2 (8).

Delphi Round 2

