Participants will score each metric using the same scale as in Round 1, and suggest revisions or comments as needed. Metrics receiving a mean score ≥ 4 by $\geq 65\%$ of each subgroup and ≤ 2 by $<20\%$ of the subgroups will be retained for voting and prioritizing in Round 3.

Delphi Round 3

Prior to Round 3, the study team will review the list of metrics, and aggregate and/or refine their wording as needed. Participants will be presented with a list of metrics with mean and standard deviation scores from the Likert scales, and be asked to vote on which metrics consist of a core set of problems (i.e., must be addressed by the health system as a priority) using a three-point scale of “definitely priority”, “equivocal (either way)”, and “not a priority” (10,20). Metrics where $>70\%$ participants voted “definite” will be marked in the publication as the core metric set. If no consensus is reached, there may be additional rounds of rating using a smaller sample of participants.

Statistical analysis

Analysis will be performed using R (R Foundation for Statistical Computing, Vienna, Austria). Cohort characteristics will be reported using descriptive statistics. Each round of Delphi will be analyzed as described above, and presented both as an overall group and as individual subgroups.

Sample size calculation

There is limited guidance regarding sample size for Delphi processes, but, in general, the key is to choose a broad representation from key stakeholders with a margin of safety built in for possible attrition. Delphi studies often involve a total of 17 members (9) and that adding more participants above 23 did not alter the consensus results (21). We have aimed for broad representation across all the key stakeholder groups. Thus, we chose $n = 20$ for each of the groups of anesthesiologists and patients. We chose the number of surgeons to represent the primary set of noncardiac surgical specialties. We also accounted for an attrition rate of 30% per literature (9,17) to ensure that there will be sufficient representation in the last cycle despite attrition.

Impact and future directions

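### The Round 1 and Round 2 retention rule cannot be applied as written: it attaches a mean score to a percentage of a subgroup and sets a 20% limit over only two subgroups

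*Combined protocol and SAP*

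**What the plan says.** Under Delphi Round 1, "Participants will independently score each of the listed metrics for importance on a five-point scale", running from 1 (not at all important) to 5 (very important). The section then provides for summaries: "The mean and median scores for each metric will be calculated for overall panel and for subgroups of 1") patients/caregivers and 2) health providers. These are to be fed back in Round 2. The retention rule follows: "Metrics receiving a mean score ≥ 4 by $\geq 65\%$ of each subgroup and ≤ 2 by $<20\%$ of the subgroups will be retained". Metrics that pass go on to the second-round vote. The Delphi Round 2 section repeats the rule in the same words to decide what goes forward to Round 3.

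Round 3 uses a different kind of rule, a plain share of voters: "Metrics where $>70\%$ participants voted" for definite priority form the core set.

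The Statistical analysis section adds no definition: "Each round of Delphi will be analyzed as described above, and presented both as an overall group and as individual subgroups".

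On panel size, the Study Population section says "We aim to recruit 77 participants with the following characteristics", of whom "26 patients and/or their family members/caregivers".

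**The concern.** The rule mixes two kinds of quantity. A mean belongs to a group: each subgroup has exactly one mean per metric. A percentage of a subgroup counts individuals, and each individual supplies one score, not a mean. The first limb therefore describes something that cannot be calculated. The second limb changes the denominator from each subgroup to the subgroups, of which there are two.

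This is the only stated retention rule in two of the three rounds, so it controls which metrics reach the core-set vote. The protocol describes no route back for a metric once dropped. An analyst who follows the word mean and one who follows the percentages could carry different lists forward. If the wording stays open, the reading could also be settled after the votes are known. The denominator of the 20% limit raises a separate question: whether low scores concentrated in one subgroup can be diluted by the other.

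**Working it through.** The 65% and 20% cut-offs are chosen thresholds, so the plan has no computed figure to reproduce. The check applies each possible reading of the rule to the same scores.

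**Inputs.** Scale 1-5, two subgroups and the thresholds come from Delphi Round 1. The panel comes from Study Population: 26 + 26 + 9 + 4 + 8 + 4 = 77, with 26 patients/caregivers. The other 77 − 26 = 51 are taken as health providers. That is an assumption, because they include 4 administrators or quality improvement leads.

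**1. Literal second limb.** The share of two subgroups meeting any condition is 0/2, 1/2 or 2/2, that is 0%, 50% or 100%. Below 20% can only mean 0 of 2. If the first limb is read as a subgroup mean of at least 4 in each subgroup, the second limb is redundant as well, since neither mean could then be 2 or less.

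**2. Share of respondents versus subgroup mean.** Neither example has any score of 2 or less.

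| Example | Subgroup | Scores | Share scoring ≥ 4 | Mean |
|---|---|---|---|---|
| A | Patients | 17 score 4, 9 score 3 | 17/26 = 65.4% | (68 + 27)/26 = 3.65 |
| A | Providers | 34 score 4, 17 score 3 | 34/51 = 66.7% | (136 + 51)/51 = 3.67 |
| B | Patients | 16 score 5, 10 score 3 | 16/26 = 61.5% | (80 + 30)/26 = 4.23 |
| B | Providers | 32 score 5, 19 score 3 | 32/51 = 62.7% | (160 + 57)/51 = 4.25 |

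Metric A is kept by share and dropped by mean. Metric B is the reverse.

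**3. The 20% limit per subgroup versus pooled, with mean deleted.** Patients: 17 score 4-5 (65.4%), 3 score 3 and 6 score 2 or less (6/26 = 23.1%). Providers: at least 34 score 4-5 and 2 score 2 or less (2/51 = 3.9%). Both subgroups pass the 65% limb. A per-subgroup limit drops the metric, because 23.1% is not below 20%. A pooled limit keeps it: (6 + 2)/77 = 10.4%.

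**4. How often the readings differ (illustration).** For each scenario, 40,000 metrics were simulated. Individual scores were normal around the metric's mean, rounded and clipped to 1-5, with the same underlying mean in both subgroups. Subgroup sizes were 26/51 (full panel) and 18/36 (about 30% attrition). Share rule: at least 65% scoring 4-5 and under 20% scoring 1-2 in each subgroup. Mean rule: mean of at least 4 in both.

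| Assumed range of metric means | Assumed SD | Readings disagree, 26/51 | Readings disagree, 18/36 |
|---|---|---|---|
| 3 to 4.8 | 0.9 | 10.4% | 10.1% |
| 3 to 4.8 | 1.1 | 9.9% | 9.2% |
| 3.5 to 4.5 | 0.9 | 18.8% | 18.0% |
| 3.5 to 4.5 | 1.1 | 16.7% | 15.9% |

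Across scenarios, retention is 40-56% by share and 28-37% by mean. Metrics kept only by share are 8.8-18.7%; kept only by mean, 0.05-0.6%. The 20% limit itself removes at most 0.53% of metrics, and pooled versus per-subgroup differs on at most 0.52%. Reruns with other random seeds agree within simulation error.

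The protocol aims for about 50 candidate metrics before the first cycle. Disagreement on 9-19% of 50 is 4.5 to 9.5 metrics in Round 1, under these assumptions.

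**The case against.** The strongest reply is that the intent is clear. Two explicit percentages are given, the first limb already points to members of each subgroup, and Round 3 is a share of participants. On that view mean is one stray word, and an analyst is unlikely to discard both percentages in order to follow it. The 0/50/100% point likewise rests on the least charitable parse, since 'of the subgroups' most naturally means their members. This is fair, and it is why a share of respondents is treated here as the likely intent. It remains an inference, however. The word mean stands in both rounds, the plan computes subgroup means that could readily be compared with 4, and the charitable parse still leaves open whether the 20% limit is per subgroup or pooled. The study cited for the rule may state it exactly, but it was not available here, and the protocol should carry its own decision rule.

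A second reply concerns weight, and much of it stands. The 9-19% depends on assumed metric means spread around the cut-off of 4. The mean-based list is almost a subset of the share-based list, so example B is a possibility and not a typical case. Metrics kept only by share must still exceed 70% in Round 3. Strongly evidenced process metrics bypass the Delphi altogether.

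The pooled-or-separate question is small in frequency. The 65% limb already caps low scores at 35% of a subgroup, so only dissent between 20% and 35% is affected. Letting the two subgroups' underlying means differ left the disagreement at about 0.5% or less at the SDs used above, and at no more than 1.9% with an assumed SD of 1.4.

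**Conclusion.** The concern holds. The only retention rule for Rounds 1 and 2 is misstated, and nothing elsewhere in the protocol corrects it. The main effect comes from the word mean: under the assumed score distributions, reading the rule as subgroup means instead of respondent shares changes about 9-19% of decisions in one round, nearly all towards dropping more metrics. The denominator of the 20% limit is a secondary matter. It rarely changes a decision, but it is a genuine choice that the text leaves open. The score distributions, SDs and ranges of means are assumptions not found in the protocol, and the 26/51 split assumes all non-patient panellists count as health providers. The effect on the final core set has not been quantified. The point should be fixed, since it concerns a decision threshold and the correction is simple.

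**What to change.** Before any Round 1 votes are seen, delete mean and restate the rule identically under Delphi Round 1 and Delphi Round 2, for example:

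> A metric is retained if, in each of the two subgroups separately, at least 65% of respondents score it 4 or 5 and fewer than 20% of respondents score it 1 or 2.

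State that means and medians are feedback to the panel only. The sponsor should confirm that a share of respondents is intended, since it is the more lenient reading in the simulation. If the 20% limit is meant for the pooled panel, that sentence should say so instead.

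With all 77 responding, the per-subgroup rule gives these cut-offs:

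- Scores of 4-5: at least 17 of 26 (0.65 × 26 = 16.9) and 34 of 51 (0.65 × 51 = 33.15).
- Scores of 1-2: at most 5 of 26 (0.20 × 26 = 5.2) and 10 of 51 (0.20 × 51 = 10.2).

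The cost is one sentence in two places and one sponsor decision on the 20% limit, with no extra data or participants.

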Introduction

Improving anesthesiology care and perioperative outcomes is a growing field encompassing quality improvement and quality assurance, research, and continuing medical education (1). With the scope of anesthesiology practice expanding further into the perioperative domain, a greater focus on postoperative recovery and longer-term outcomes is warranted (2). Multiple consensus initiatives have standardized perioperative endpoints (3–5). However, no core list of metrics exists to evaluate the quality of Canadian anesthesia, perioperative care, and acute pain management in the context of a broad range of existing patient-reported outcome and experience measures, quality and safety indicators, process metrics, and practice standards.

With the increasing adoption of Anesthesia Information Management Systems, Electronic Health Records, and patient-facing virtual care platforms, we have the opportunity to routinely and systematically collect patient-reported and system-collected data to measure anesthesiology performance. By enabling personalized feedback and learning health system approaches, a standardized set of metrics may provide the foundation for further targeted research and interventions to improve anesthesia, perioperative care, and acute pain management for Canadians (1). In this study, we will engage a diverse, multidisciplinary panel to answer the question: what defines quality in anesthesiology, perioperative medicine, and acute pain management in Canada, and how should we quantify it?

Objectives

The overall objective is to develop a consensus list of metrics which can be used to evaluate the quality of anesthesia, perioperative care, and acute pain management for adults undergoing inpatient non-cardiac surgeries that can be used for quality improvement and quality assurance, research, and continuing medical education in the Canadian care context.

The specific metrics will be obtained using the following approach:

1. Obtain a list of candidate metrics through a scoping literature review. For each metric, information will include a) definition(s), b) studies on validity/feasibility and level of evidence, c) timing of measurement, and d) population(s) studied

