2. All outcome metrics, as well as process/structure metrics that have limited supporting evidence, will go through a multidisciplinary modified Delphi consensus process, using surveys, to 1) select and mark the importance for each metric, and 2) select a core set of the most important metrics.

Development of a standardized set of core metrics to assess the quality of anesthesia, perioperative care, and acute pain management in Canada: scoping review and multidisciplinary consensus Delphi study

Methods

Study Design Overview

First, the steering committee will conduct a scoping review of the literature to obtain a list of metrics that have been validated and/or are in clinical use to evaluate anesthesia, perioperative care, and acute pain management, to use as a starting point for the modified Delphi process. Then, following approval from the University of British Columbia Research Ethics Board and with written informed consent from participants, a multidisciplinary panel will identify the most important metrics using a modified Delphi process, in accordance with existing literature including the Core Outcome Set-STAndards for Development (The COS-STAD) recommendations (3,6–11). In the last Delphi cycle, the panel will be asked to select the most essential items into a core set of metrics.

Stage 1. Scoping Review

We will first conduct a scoping review according to the Preferred Reporting Items for Systematic Reviews and Meta-Analyses extension for scoping reviews (PRISMA-ScR) (12) and the Joanna Briggs Institute methodology for scoping reviews (13). The purpose of this scoping review is to explore the evidence on the use of metrics to assess the quality of anesthesia, perioperative care, and acute pain management as reflected in the literature. A scoping review has been selected as the methodology of choice for this review because standardized metrics in perioperative care are an emerging area of research. The scoping review was registered on 2022-03-21 as <https://doi.org/10.17605/OSF.IO/8BNVW>.

Search strategy

The metrics included in our scoping review are patient-reported outcome and patient-reported experience measures, patient satisfaction, quality indicators, safety indicators, practice guidelines, process metrics, and other existing metrics. An initial search (Appendix 1) of MEDLINE (Ovid) was co-developed with guidance by a research librarian ([name]).

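### The Round 3 vote is described as picking problems for the health system to address, which contradicts the stated task of choosing the metrics essential for evaluating quality

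*Combined protocol and SAP*

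**What the plan says.** The Objectives set out to "develop a consensus list of metrics which can be used to evaluate the quality of anesthesia, perioperative care, and acute pain management". The second item of the approach listed there gives the Delphi two jobs: rating the importance of each metric, and choosing a core set of the most important ones.

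The task of the last cycle is stated twice. In the Study Design Overview, "the panel will be asked to select the most essential items into a core set of metrics". In the Delphi process section, "In the last Delphi cycle, the panel will be asked to select the most essential items to include into a core set of metrics". The latter section also says that the voting "will be used to identify the most important metrics to define the quality of anesthetic care".

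Rounds 1 and 2 score each metric for importance from 1 to 5. The Round 2 section sends the survivors on for voting and prioritizing.

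The Delphi Round 3 section is the only operational description of the final vote. Panellists see the surviving metrics with mean and standard deviation scores and are asked to "vote on which metrics consist of a core set of problems (i.e., must be addressed by the health system as a priority". They answer on a "three-point scale of “definitely priority”, “equivocal (either way)”, and “not a priority". Metrics for which more than 70% of "participants voted “definite” will be marked in the publication as the core metric set".

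One group of metrics does not depend on this vote. Under Inclusion and exclusion of metrics, process indicators with a high level of trial evidence, such as Grade 1a, join the final and core lists without passing through the Delphi.

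**The concern.** Whether something needs fixing and whether it needs measuring are different questions. A serious complication that is already well controlled may be essential to monitor, because deterioration would otherwise go unseen, yet a panellist could honestly answer that it is not a problem the system must tackle first.

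If the survey follows the Round 3 description, the vote that confers core status asks about need for action, while the published product is presented as the metrics most essential for judging quality. Votes cast on one question cannot be reinterpreted afterwards as answers to the other, so a mismatch found after Round 3 could be repaired only by voting again.

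**Working it through.** The protocol gives no figure for this point, so the check is mainly a comparison of text.

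1. **Compare the questions.** The Objectives, the Study Design Overview and the Delphi process section all concern metrics, and whether they are essential or important for evaluating quality. The Round 3 section concerns problems, and whether the health system must address them.

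2. **Look for a bridge.** No section defines 'problems' or says that being addressed by the system means being measured. The Impact and future directions section points the other way: it speaks of outcomes to measure, and its next step is to find the best measures for the core set.

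3. **Locate the conflict.** It lies in the noun 'problems' and in the explanatory clause that follows it. That clause also shifts the actor. The metric selection criteria require direct anesthesiologist involvement for process metrics and drop structural indicators that individuals or departments cannot change, whereas the Round 3 wording refers to the health system. The word 'priority' in the response labels is not by itself a conflict, since prioritizing is a declared aim of Round 3.

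4. **Check the rule against the scale.** The scale's top label is 'definitely priority', but the decision rule counts votes for 'definite'. The intended category is easy to guess, but the two should match.

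5. **Count the votes that decide.** The Study Population list gives 26 + 26 + 9 + 4 + 8 + 4 = 77. More than 70% of 77 means more than 53.9, so at least 54 votes. After 30% attrition, 77 × 0.70 = 53.9, or 53 whole panellists. More than 70% of 53 means more than 37.1, so at least 38. (With 54 panellists the bound is 37.8, again 38.) These counts show what core status requires. They hold under any ballot wording and do not measure the defect.

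6. **See whether an effect size can be derived.** Let e be the share who think a metric essential to measure, f the fraction of those who do not see it as a problem to be addressed, and g the fraction of the rest who do see it as one. If panellists answer the question as written, the top-category share is e(1 − f) + (1 − e)g. The documents give none of these three values. Purely as an assumption, take e = 0.80 and g = 0:
   - f = 0.10: 0.80 × 0.90 = 0.72, and the metric stays in.
   - f = 0.125: 0.80 × 0.875 = 0.70, and it falls out, because the rule requires more than 70%.
   - f = 0.25: 0.80 × 0.75 = 0.60, and it falls out.

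   A value of g above zero raises the share, so even the direction is not fixed. The range shows that wrong omission is possible, not that it is likely.

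**The case against.** The strongest reply is that this is a drafting slip in a one-sentence summary. The REDCap item is not in the documents, and the intended task is stated correctly in two other sections. The Round 3 sentence itself presents metrics and asks which metrics qualify, and the next sentence calls the result a core metric set. The response scale is also supported by two cited sources, so the priority labels may be deliberate.

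Much of this stands. One might infer that panellists will certainly be asked the wrong question, but the documents show only that the specification contradicts itself. One might also infer that the priority labels are wrong in themselves. They are not: they become ambiguous only because the clause before them says priority for what.

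A further reply is that every item on the ballot has already passed two rounds of importance scoring, with thresholds in both the patient/caregiver and the health provider subgroups. This too stands, and it rules out the inference that the published set would simply be a list of perceived problems. It would be a subset of metrics already rated important. An urgent resourcing issue that makes a poor metric is largely screened out by the earlier rounds and by the exclusion of structural indicators. What remains is the risk of omitting a metric that is essential to monitor but seen as already well handled.

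The reply does not remove the contradiction. The Round 3 section is the text from which the survey would be built. A panel that includes 26 patients or caregivers cannot be assumed to read 'problems' as 'essential to measure', and showing them earlier importance scores does not change the question put to them.

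**Conclusion.** The contradiction is real and sits in the voting question behind the core-set rule. For every metric that goes through the Delphi, core membership rests on this vote, so the wording needs correcting before Round 3 opens. If the ballot is built as written, some metrics that panellists regard as essential to measure could be wrongly left out. How many, if any, cannot be computed from the documents.

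A reader might infer that the whole published result hangs on this one item. The documents do not support that. Grade 1a process indicators enter the core list without a vote, the Delphi also reports importance ratings, and additional rounds are allowed if objectives or consensus are not reached.

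The conclusion assumes that the survey would follow the Round 3 section literally. If the ballot already asks which metrics are essential to a core set, only the protocol text needs correcting.

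**What to change.** Before Round 3, remove the wording about problems to be addressed by the health system and put a question that matches the Objectives and the two statements of the last-cycle task. For example: *Is this metric essential to include in the core set for evaluating quality of care?*, with the three care areas named in the Objectives spelled out.

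Keep the three-point scale, but anchor its labels to that question, for example with *definitely a priority for the core set* or *definitely core* as the top label and the other two worded to match. State the more-than-70% rule in terms of that exact top label.

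The cost is survey and protocol wording only. The panel, the number of rounds and the threshold do not change.

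### If Round 3 reaches no consensus, an undefined smaller sample may decide core-set membership; the extra round should go to the whole remaining panel

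*Combined protocol and SAP*

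**What the plan says.** **Extra rounds.** The Delphi process section allows cycles beyond the third if the objectives have not been met, and does not say who would take part. Delphi Round 3 is more specific: "there may be additional rounds of rating using a smaller sample of participants". Neither place gives the sample's size, its mix of stakeholders or how it would be chosen.

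**Who is meant to decide.** The Delphi process section says: "In the last Delphi cycle, the panel will be asked to select the most essential items to include into a core set of metrics". It also says: "The participant who missed a round will still be able to participate in future rounds". The Sample size calculation section allows for 30% attrition "to ensure that there will be sufficient representation in the last cycle despite attrition".

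**The core label.** In Rounds 1 and 2 a metric must meet a threshold in each of two subgroups, patient/caregiver and health provider. Metrics that pass Round 2 "will be retained for voting and prioritizing in Round 3". Round 3 uses a different, three-point priority scale. Metrics that more than 70% of participants rate a definite priority "will be marked in the publication as the core metric set", with no subgroup condition. The Statistical analysis section says each round will be "presented both as an overall group and as individual subgroups". Grade 1a process indicators enter the core list without a vote and are outside this point.

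**The concern.** The core set is the study's main product, and its authority comes from a broad multidisciplinary panel that includes people with lived surgical experience. Recruitment was enlarged to protect that breadth up to the last cycle. The fallback allows the metrics still open to be settled by a subset about which nothing is fixed in advance. Such a subset could hold few patients/caregivers, or none. Because the plan does not say when it would be chosen, it could be chosen with the Round 3 votes already in view.

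The secondary issue is that cross-group agreement, which appears to be required for importance in Rounds 1 and 2, is not required for the final priority label. A reader of the published list could not tell from the label alone whether both subgroups supported a metric.

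**Working it through.** **1. Panel (Study Population).** 26 anesthesiologists + 26 patients/caregivers + 9 surgeons + 4 nurses + 8 physicians + 4 administrators or quality leads = 77, which matches the plan's total. Patients/caregivers: 26. Others: 77 − 26 = 51. I assume all 51 form the second subgroup, since the plan names only two.

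**2. Votes needed for the label.** The smallest whole number above 70% of N is floor(0.7 × N) + 1.
- All 77 voting: 0.7 × 77 = 53.9, so 54.
- Equal 30% attrition (assumed): 51 × 0.7 = 35.7, about 36; 26 × 0.7 = 18.2, about 18. Then N = 54, 0.7 × 54 = 37.8, so 38.

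**3. What the fallback changes.** The subset's size is not stated, so this is only an illustration. Suppose it had 17 members, the figure the plan cites as common for Delphi panels. Then 0.7 × 17 = 11.9, so 12 votes would confer the label, against 38 of 54. In proportion to the panel it would hold 17 × 26/77 = 5.7, about 6 patients/caregivers. Nothing in the plan requires that proportion.

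**4. What the pooled rule allows (full panel, 54 votes needed).**

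| Others in favour | Patients/caregivers needed |
|---|---|
| 42 of 51 (82%) | 54 − 42 = 12 of 26 (46%) |
| 46 of 51 (90%) | 54 − 46 = 8 of 26 (31%) |
| 51 of 51 | 54 − 51 = 3 of 26 (11.5%) |

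The others cannot reach the threshold alone: 51/77 = 66.2%, or 36/54 = 66.7% after equal attrition. In the other direction, unanimous patients/caregivers still need 54 − 26 = 28 of 51 others (55%).

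**5. What a binding subgroup majority would do.** Model: X ~ Bin(patients/caregivers, p₁), Y ~ Bin(others, p₂), independent. The pooled rule is X + Y > 0.7N. The binding version adds more than half in each subgroup. All support rates are assumed.

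| Voters (others + patients/caregivers) | Support (others / patients/caregivers) | Pooled | With majority in each |
|---|---|---|---|
| 51 + 26 | 90% / 40% | 0.804 | 0.108 |
| 51 + 26 | 80% / 40% | 0.274 | 0.082 |
| 36 + 18 | 75% / 75% | 0.828 | 0.823 |
| 36 + 18 | 90% / 60% | 0.977 | 0.735 |
| 36 + 18 | 90% / 55% | 0.955 | 0.576 |

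The first two rows show what the pooled rule lets through, mainly when support among the others is about 85% or more. The last two show the price of a binding condition: metrics that a true patient/caregiver majority supports often lose the label, because about 18 voters give a noisy proportion.

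**The case against.** **On the fallback.** The representation sentence justifies the attrition allowance and does not govern an optional extra round. The last Delphi cycle can naturally be read as Round 3. Both points stand, so a reader who infers that the plan contradicts itself goes too far. It is also an inference that the subset would be picked after the votes are seen. What remains is that the plan allows an undefined subset to settle core membership, which works against its own stated aim.

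**On the pooled label.** A reader might infer that Round 3 is in error for dropping the subgroup condition, or that non-patient members can impose a core set. The documents support neither.
- Round 3 asks about priority, not importance, and a different rule for a different question is legitimate. The Delphi process section says: "While specific guidance on consensus thresholds and the optimal scales are limited".
- No section promises a subgroup condition on the label.
- Every voted metric has already passed the earlier filter twice, and subgroup results will be presented.
- The others cannot exceed 70% alone on the planned panel. They could only if patients/caregivers dropped out disproportionately (assumed example: 51 others and 21 patients/caregivers, 51/72 = 70.8%).
- The contrast with Rounds 1 and 2 depends on reading their rule as a percentage of members within each subgroup. The wording, a mean score reached by a percentage, is ambiguous.

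The earlier filters do not fully answer the point, since rating a metric important is not the same as voting it a definite priority.

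**Conclusion.** The fallback is worth changing. It leaves the deciding group undefined at the step that can complete the core set, and the remedy is cheap. It is a modest improvement to the plan and does not invalidate the study. How much the fallback would matter cannot be computed, because neither the subset nor the number of metrics left open is known.

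The pooled label is a design choice with a transparency gap. On the full panel a metric can become core with 46% of patients/caregivers in favour if 82% of the others agree. How often that would happen rests on assumed support rates that the documents do not give. A binding subgroup threshold is optional and not recommended as a requirement: at an assumed 90%/60% support with 36 + 18 voters it cuts the chance of a core label from 0.977 to 0.735.

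**What to change.** **Extra round.** Replace the fallback sentence in Delphi Round 3 with: *Where Round 3 ends without consensus, one additional round, covering only the metrics without consensus, will be sent to all panel members who have not withdrawn, and the same rule of more than 70% will apply.* Align the general sentence on additional cycles in the Delphi process section with this. State before Round 3 opens what counts as a metric without consensus, since the plan does not define it.

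Cost: one more REDCap round for the panel, with the notice, two-week window and reminders already described. The limit of one round prevents repeated voting until a metric passes.

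**Core label.** Keep the pooled rule. Add: *In the published core list, any voted metric for which half or fewer of the voters in either subgroup chose the top priority category will be marked, with the share in each subgroup.* State that the two subgroups are patients/caregivers and all other panel members.

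Cost: one sentence and a table footnote. No new data are needed, because subgroup results are already to be presented.
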